# 3 OBJECTIVES

The primary Phase II investigational objective is to show a differential effect on the pre-to-post-intervention change in upper extremity (UE) motor function between an interventional group receiving the MOVE-IT home exercise program (HEP) and a usual care treatment (UCT) group, as assessed by the Jebsen Taylor Hand Function Test (JTHFT) and other gold-standard clinical assessments of UE function.

Blinded assessors, certified for the study instruments, will evaluate children in both groups at pre-treatment (baseline), immediate post-treatment (baseline + 10 weeks), and 3 months post-treatment. Assessments (3 total) will take place in an outpatient setting and include the following blinded instruments:

- Jebsen Taylor Hand Function Test (JTHFT) (primary outcome measure)
- Quality of Upper Extremity Skills Test (QUEST) (dissociated movements and grasp components)
- Wolf Motor Function Test (WMFT)

Additionally, parents will be asked to complete the following parental report instrument during each assessment visit:

• Pediatric Motor Activity Log (inventory of child's functional use of the UE)

For both groups, parents will be asked to maintain a weekly activity log, including activities performed under the MOVE-IT intervention and any other therapy a child might receive.

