#### MOVE-IT HEP Independent Practice at Home

- Participants will be asked to employ the GRASP system for UE practice at home for a total of 1 hour/day, 5 days/week over the 10-week intervention period.
- Patients will continue to perform any previously prescribed therapy.

- Once per week during this period, non-blinded study staff will employ an authorized web application on a UVA computing system to remotely monitor de-identified participant data (see Data Security Plan for details) that includes exercise adherence (duration performed), movement repetitions accomplished (exercise reps), and exercise intensity (speed).
- At least once every two weeks, non-blinded study staff will contact the participant by phone or HIPAA compliant video conferencing to collect self-reported adherence data and confirm that no change in medical status has occurred that would impact continued participation.

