#### **GROUP 2: UCT GROUP:**

- Participants in the control group will continue to receive any previously prescribed therapy services. These patients will not receive any treatment services through the study as UCT group participants.
- At least once every two weeks during the interventional period, non-blinded study staff will contact the participant by phone or HIPAA compliant video conferencing to collect self-reported adherence data and confirm that no change in medical status has occurred that would impact continued participation.

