#### 7.4 Analysis Plan

Primary variable analysis involves analysis of completion times for each of the seven tasks in the JTHFT which will be summed to produce a total score. The pre-intervention scores will be subtracted from the post-intervention scores to produce a set of delta values. These delta values scores ( $\Delta$ ) will be analyzed via Analysis of Covariance (ANCOVA). One null hypothesis will test if the mean pre-to-post-intervention change in the total JTHFT score is equal to zero, while the second null hypothesis will test if the mean pre-to post-intervention change in the JTHFT score is the same for patients who participate in a 10-week MOVE-IT HEP and patients who under UCT over the same duration. For both null hypotheses, a p $\leq$ 0.05 decision rule will be utilized as the rejection criterion. Analysis of data from the 3-month follow-up assessment will be performed in a similar manner.

Secondary variable analysis includes analysis of the pre-to-post intervention changes in the composite WMFT scores which will be analyzed in the same way as the pre-to-post intervention change in the composite JTHFT scores. The same method of analysis will be used to analyze the pre-to-post intervention changes in the QUEST scores.

The Likert scale responses to the SUS questionnaire will be summarized per question, and per question category, by frequencies and percentages. As an overall measure of system usability, a composite SUS score in the range from 0 to 100 will be derived from individual responses. By convention, a SUS score greater than or equal to 68 is indicative of an efficient, effective, and satisfying system. For the TAM questionnaire, percentages of favorable responses to the questions of each topic will be estimated via a binomial generalized estimating equation model, and a 90% confidence interval constructed. A Wald test will be used to test the null hypothesis that the odds of a favorable response are independent of the question topic.

Therapy session adherence and activity will be assessed by way of a binomial generalized estimating equation model, in which therapy adherence and activity measures (collected via parental logs) will be compared between the patients who participate in a 10-week MOVE-IT HEP and patients under UCT over the same duration.

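### Adherence is compared between arms from parental logs without a definition or denominator, and no analysis is specified for the system-recorded MOVE-IT use data

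*Combined protocol and SAP*

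**What the plan says.** Section 7.4 (Analysis Plan) sets the method: "Therapy session adherence and activity will be assessed by way of a binomial generalized estimating equation model". The source and contrast follow in the same sentence: "therapy adherence and activity measures (collected via parental logs) will be compared between the patients" in the HEP and UCT arms over the 10 weeks. It gives no definition of adherence, no binary outcome and no denominator.

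The arms are asked to do different things. Section 6.1 asks HEP children to practise "for a total of 1 hour/day, 5 days/week over the 10-week intervention period". For UCT it says "These patients will not receive any treatment services through the study as UCT group participants". Prior therapy continues in both arms: "Participants in the control group will continue to receive any previously prescribed therapy services" for UCT, and "Patients will continue to perform any previously prescribed therapy" for HEP. Staff contact both arms at least every two weeks for self-reported adherence; for UCT, what is being adhered to is not stated.

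Under Section 3, the weekly parental log in both groups covers "activities performed under the MOVE-IT intervention and any other therapy a child might receive". In HEP, staff also review system data every week, covering "exercise adherence (duration performed), movement repetitions accomplished (exercise reps), and exercise intensity (speed"). Section 8 lists game-derived duration and repetitions as a research data source, separate from the weekly logs. Section 7.4 does not mention them.

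**The concern.** The case for MOVE-IT rests on dose. Section 2.2 argues from studies of constraint-induced movement therapy (CIMT) that 60 hours was sufficient and 30 was not, and that 50 to 60 hours are needed in practice. Two facts are therefore needed to read the Jebsen Taylor Hand Function Test (JTHFT) result: how much MOVE-IT practice HEP children did, and whether the arms differed in other therapy. Section 5.2 places no restriction on other treatments, and Section 7.3 expects some children to receive them.

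Without the first, a null result cannot be divided between an ineffective system and under-delivery. Without the second, a positive result cannot be separated from co-intervention. The planned analysis answers neither question directly, and it relies on reports from parents who know the assignment even though an objective record exists for HEP.

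**Working it through.** **The plan's own figures.** No expected rate, power or sample size is stated for the adherence analysis, so there is nothing to reproduce there. The figures in Section 7.2 do reproduce. With 40 completers and a probability of 0.75, Noether's formula gives Φ(√(12 × 0.5 × 0.5 × 40) × 0.25 − 1.960) = Φ(2.739 − 1.960) = 0.782, two-sided. A simulation with normal data (20,000 runs) gives 0.810, against the stated 0.80. For dropout, 20 / 0.85 = 23.5, rounded up to 24 per group. None of this depends on the adherence analysis.

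**Step 1: denominators.** HEP (Section 6.1): 5 days x 10 weeks = 50 practice days, and 50 x 1 hour = 50 hours. One practice day is counted here as one session, which the protocol does not say. UCT: 0 study-assigned sessions, plus prior therapy in an amount that is not given, varies by child and may be zero. HEP children also have prior therapy. A share of assigned sessions would thus mean MOVE-IT use (perhaps with prior therapy) in HEP, and prior therapy alone in UCT.

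**Step 2: what a pooled comparison can show.** Let M be MOVE-IT hours and O be other therapy hours. The log totals are M + O(HEP) and O(UCT), so the difference is M + [O(HEP) − O(UCT)]. By design M can add up to 50 hours. As an illustration, an observed difference of 40 hours fits all three of these:

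- M = 50, with other therapy 10 hours lower in HEP (50 − 10 = 40)
- M = 40, with other therapy balanced (40 + 0 = 40)
- M = 30, with other therapy 10 hours higher in HEP (30 + 10 = 40)

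The total shows how far apart the arms were in therapy received. It does not give M, and it does not show whether O was balanced.

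**Step 3: why the delivered dose matters.** Under assumed adherence, 100% gives 50 hours, 80% gives 50 x 0.8 = 40, and 60% gives 50 x 0.6 = 30. Only full adherence reaches the lower end of the 50 to 60 hours in Section 2.2. That range comes from the discussion of CIMT; the protocol does not set it as an adherence threshold for MOVE-IT.

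**Step 4: the data at hand.** The system records duration for every HEP child. The ceiling is 24 x 50 = 1,200 assigned sessions if all recruited children stay, or 20 x 50 = 1,000 for the planned completers. The logs can give O in both arms if MOVE-IT entries are separated out.

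**The case against.** The strongest reply is that the analysis is under-specified rather than wrong. Much of that stands.

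- A reader might infer that UCT has nothing to adhere to, so the contrast cannot be computed. The documents do not support this. UCT children may have prescribed therapy, and Section 6.1 plans to collect adherence reports from their families.
- A reader might infer that a binomial model is unsuitable. It need not be. A GEE can model a weekly yes/no outcome, such as any therapy logged that week, with the same 10 weeks in both arms. Section 7.4 does not say that this is meant.
- A reader might infer that comparing total logged activity is uninformative. It is not: low HEP uptake or heavy outside therapy in UCT would shrink the difference, so it measures dose separation.
- A reader might infer that the system data will be ignored. The documents show only that no analysis is specified; the data are monitored weekly and listed as research data.
- A reader might suppose that parents over-report by some known amount. The documents give no figure, and the point does not need one.

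The logs are also the only source common to both arms, and other therapy is further recorded at assessment visits (Section 4) and prospectively from parents (Section 7.3). That supports a between-arm comparison of other therapy. It does not make the log the best source for MOVE-IT use in HEP, and Section 7.4 does not separate the two components.

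**Conclusion.** The point holds as a cheap improvement to a supportive analysis. Section 7.4 leaves adherence and its denominator open where the arms have 50 and 0 study-assigned sessions. It names pooled, unblinded self-report as the only source, and it specifies no analysis of the recorded HEP use. Followed as written, it would give neither a reliable delivered MOVE-IT dose nor a check of co-intervention balance.

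A reader might infer that the trial's main conclusion is compromised. It is not: the primary JTHFT test, the power and the sample size do not depend on this analysis, and the data to repair it are already being collected. What is at stake is how well the primary result can be interpreted.

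The conclusion assumes that one practice day counts as one session and that log entries can be divided into MOVE-IT and other therapy. No numerical bias is claimed.

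**What to change.** Amend Section 7.4 before outcome data are examined:

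1. Estimate HEP adherence from system-recorded sessions and hours against the 50 assigned, as a single-arm estimate with a confidence interval. Define a session, and say how the 50 applies to a child who withdraws. Use the parental log as a cross-check, and flag any gap in the system data that is filled from it.
2. Compare non-study therapy (logged hours excluding MOVE-IT) between arms as a check of co-intervention balance. Keep total therapy received as a descriptive measure of dose separation.
3. If the binomial GEE is kept for a between-arm comparison, state its binary outcome and denominator so that both mean the same in HEP and UCT.

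The cost is analysis-plan wording and a little programming. No new visits, participants or instruments are needed, provided the log separates MOVE-IT from other therapy. The small downside is that system data may have gaps, which is why the log stays as a flagged back-up.

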#### 4 STUDY DESIGN

The study is a randomized control study.

Following screening, enrolled subjects will be randomized to either the MOVE-IT home exercise program (HEP) or usual care treatment (UCT) group using a centralized and masked process developed by the study biostatistician. The HEP group is the interventional group. The UCT group is the control group. Following the control strategy previously adopted in the Children with Hemiparesis Arm and Movement Project (CHAMP) multi-site RCT (NICHD R01, trial registration number NCT01895660), children in the UCT group will be followed as they continue to receive their previously prescribed therapy services. As UCT group participants, these children will not receive any treatment services through the study. Parents will be asked to report therapy services their children receive during each assessment visit.

To ensure that an approximately equal number of subjects are randomized to the MOVE-IT HEP and UCT groups throughout the Phase II enrollment period, we will randomly assign the patients to the two study-groups in accordance with a permuted block randomization scheme. The randomization list will be generated by a UVA study biostatistician ([name]) using the PLAN procedure of SAS (SAS Institute Inc., Cary, NC). One subject randomization table will be generated for each site. The group assignment will be blinded to the therapists (raters) who perform the pre- and post-assessments. The group assignment will be not be blinded to the participants. The non-rater members of the IRB-approved study team will have access to the randomization list.

Demonstration of statistically significant improvement in UE motor function for participants the MOVE-IT HEP versus UCT will support the validity of MOVE-IT use as an intervention for children with hemiplegia. In home use, MOVE-IT will enable more frequent and intensive therapy with reduced travel and may extend the service range of existing rehabilitation providers to include underserved areas. In clinical practice, MOVE-IT will enable new models of delivery based on remote monitoring combined with outpatient services, increasing quality and efficiency of care. Statistical considerations for sample size determination, primary analysis, and secondary analyses are described below.

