All biostatistical design and analysis will be conducted by [name], a Pstat accredited Senior Biostatistician within the Department of Public Health Sciences of the University of Virginia School of Medicine.

Data from the UVA and Duke sites will be combined during analysis. Randomization will be done at each site. Variation between the two sites is expected to be minimal. The effect of the treatment to be tested is expected to be the same among the two sites, which

will use identical protocols.

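### Site is a randomization stratum, but the section 7.4 ANCOVA names no site term; if mean change differs between sites, the standard error is overstated and power is lost.

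*Combined protocol and SAP*

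**What the plan says.** Section 4 (Study Design) describes the allocation: "we will randomly assign the patients to the two study-groups in accordance with a permuted block randomization scheme", and "One subject randomization table will be generated for each site". Allocation is therefore stratified by site.

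Section 7.4 (Analysis Plan) sums the JTHFT task times, takes post minus pre, and says that the resulting change scores "will be analyzed via Analysis of Covariance (ANCOVA"). No covariate is named. WMFT, QUEST and the 3-month follow-up are to be handled in the same or a similar way.

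At its end, section 7.4 says: "Data from the UVA and Duke sites will be combined during analysis. Randomization will be done at each site". It gives two reasons. The first is "Variation between the two sites is expected to be minimal". The second is "The effect of the treatment to be tested is expected to be the same among the two sites", on the ground that both sites follow the same protocol. No site term, stratified analysis or by-site display appears anywhere in the document.

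**The concern.** A factor used to stratify the randomization normally belongs in the analysis model, because otherwise the standard error ignores the balance that the stratification created.

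The two reasons in section 7.4 do not settle the matter. A common treatment effect justifies leaving out a treatment-by-site interaction, but says nothing about the site main effect. The expectation of little site variation does bear on the main effect, but no data in the document support it.

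A constant site or rater offset cancels in a change score, so only a site difference in mean change, after any covariates, matters. Such a difference is possible: the trial takes children aged 4 to 14 with MACS levels II to V (sections 5.1 and 5.2), and they continue their existing therapy (section 6.1).

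Two things are at stake: power in a trial that plans on 40 completers, and a clear statement of the primary model. An ANCOVA with no named covariate, together with the statement that sites are combined, lets two analysts fit different models.

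**Working it through.** **Inputs from the document**
- 20 completers per group, 40 in total; power at least 0.80 for a Wilcoxon Mann-Whitney test if the probability that a MOVE-IT change exceeds a UCT change is 0.75 (section 7.2).
- About 24 children per site (section 7.3) and roughly equal arms (section 4).
- Alpha: "0.05 decision rule will be utilized as the rejection criterion" (section 7.4).

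**Assumptions**
- Two-sided test; normal change scores with within-site SD 1.
- 10 completers per arm per site (40 / 4). Exact balance is an idealisation: block size is not stated and attrition may be uneven.
- The site gap g in mean change, in within-site SD, is not in the document and is varied.

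**Step 1: the plan's own figure.** Noether's formula gives N = (1.960 + 0.842)² / (12 × 0.25 × 0.25²) = 41.9. At N = 40, power is Φ(√(40 × 3 × 0.25²) − 1.960) = 0.782. Simulating the Mann-Whitney test under a normal shift gives 0.814. The stated 0.80 is reproduced to within about two points.

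**Step 2: effect on the linear-model scale.** d = √2 × z(0.75) = 0.954 SD. The standard error is √(2/20) = 0.316. With no site gap, exact noncentral-t power is 0.8363 without site (38 residual df) and 0.8358 with site (37 df). Including site needlessly costs 0.0005.

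**Step 3: leaving site out when the sites differ.** With exact balance the treatment estimate is identical in both models. What changes is the residual variance. Without site, its expectation is 1 + (40 × g²/4)/38 = 1 + 10g²/38, so the standard error is inflated by about √(1 + 10g²/38). At g = 1.0 this is √1.263 = 1.124. The share of variance due to site is (g²/4)/(1 + g²/4).

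Simulation, 200,000 trials per row:

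| Assumed gap (SD) | Variance due to site | SE ratio, without / with site | Type I error without site | Power without site |
|---|---|---|---|---|
| 0.25 | 1.5% | 1.008 | 0.048 | 0.833 |
| 0.46 | 5% | 1.028 | 0.044 | 0.823 |
| 0.67 | 10% | 1.057 | 0.038 | 0.808 |
| 1.0 | 20% | 1.125 | 0.029 | 0.767 |

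With site in the model, type I error is 0.049 to 0.050 and power 0.836 to 0.837 in every row. Power without site equals 0.80 at a gap of 0.734 SD (12% of variance). A separate simulation of 100,000 trials per scenario agrees: at gaps of 0.5, 0.75 and 1.0 SD, power without site was 0.820, 0.796 and 0.769, against 0.834 to 0.837 with it.

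**Step 4: two checks.** Adding a baseline covariate to both models (assumed slope −0.3, residual SD 1) gives SE ratios of 1.008, 1.027, 1.056 and 1.124, essentially unchanged. If dropout left arms of 11 and 9 at one site and 9 and 11 at the other, the estimate without site would shift by g × (11/20 − 9/20) = 0.1g. That is 0.05 SD at a gap of 0.5 and 0.10 SD at a gap of 1.0, and either direction is possible. The model with site showed no such shift.

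**The case against.** The case for leaving the plan alone is reasonable. There is no validity failure: with balanced arms the estimate and its true sampling spread are the same with or without site, and the only harm is an overstated standard error. The loss is under 2 power points for gaps up to about 0.5 SD. The 0.73 SD gap needed to bring power to 0.80 is about 77% of the treatment effect itself (0.734 / 0.954), and nothing in the document suggests a gap that large. The sites use identical procedures (section 6.1) and certified assessors (section 3). Combining data need not exclude a site term. The wider gap is that no covariate is named at all, baseline JTHFT included. Finally, the stated 0.80 belongs to a Mann-Whitney test, while 0.836 and the 0.73 SD crossing come from a linear model.

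Most of this stands as a limit on size. The loss is conditional and modest, the 0.73 SD crossing is illustrative, and the baseline check fixes the residual SD, so its agreement is partly built in. None of it argues for omitting site. Identical procedures do not guarantee that the children at the two sites change alike, and protection against a gap costs one degree of freedom. That the wording could be read either way is itself a reason to state the model.

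**Conclusion.** The concern holds. Site is a stratum, section 7.4 names no site term, and the reasons it gives do not justify omitting the site main effect. If the sites change alike, the consequence is negligible. If they differ, the standard error is overstated by about 1% to 12% over assumed gaps of 0.25 to 1.0 SD. The test becomes conservative, and power falls by less than 1 point at the low end and about 7 points at the high end. These figures assume normal change scores, a two-sided 0.05 test, d = 0.954, a common treatment effect and exact balance within site; the gaps are assumptions throughout. The change is worth making because it costs almost nothing, but the plan's validity does not depend on it.

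**What to change.** In section 7.4, after the statement that the sites will be combined, add:

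> The ANCOVA models for JTHFT, WMFT and QUEST (post-treatment, and the 3-month follow-up analysis) include site (UVA/Duke, the randomization stratum) as a fixed covariate alongside treatment and any other prespecified covariate. The treatment effect is also shown by site, descriptively.

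The reference to other covariates prevents the sentence from being read as excluding the baseline score. The by-site display is a simple look at the common-effect assumption, not a test of it; with about 10 completers per arm per site it will be imprecise.

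The cost is one or two sentences and one residual degree of freedom (38 to 37). Site is known for every child, so no new data are needed, and the combined analysis is kept.
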